1.3 Unmet Need in DME and RVO: Less Frequent Injections

Despite the effectiveness of IVT anti-VEGF agents to reduce the edema associated with DME/RVO, treatment requires frequent IVT injections to manage these often-chronic conditions – approximately every 4 to 8 weeks. An international survey of retinal specialists reported that the most significant unmet need in managing retinal disease are long-acting sustained drug delivery to reduce the treatment burden for both patients and physicians (ASRS 2016).

To address the unmet medical need in patients with DME and RVO, Graybug Vision has developed a proprietary drug product (GB-102) intended to reduce the frequency of IVT injections (once every 6 to 12 months) and provide a mechanism of action involving blockade of multiple VEGF receptor targets associated with angiogenesis, vascular permeability, and cellular proliferation, which are key biologic processes associated with the progression of macular edema seen in DME and RVO.

[figure not shown]
1.4 Investigational Product

GB-102 is a depot formulation of sunitinib malate intended for IVT injection. The formulation consists of microparticles made from poly(lactic-co-glycolic) acid (PLGA) and methoxy-polyethylene glycol (mPEG)-PLGA. The mPEG component provides a hydrophilic, biocompatible property. During production, the microparticles are surface treated to facilitate their aggregation upon IVT injection to form an implant-like depot in the vitreous. After IVT injection, the microparticles degrade into lactic acid, glycolic acid, and mPEG. GB-102 has been engineered to deliver therapeutic doses of sunitinib for at least 6 months with a single 50- μ L IVT injection based upon clinical data, theoretically enabling dosing twice yearly as described in [Section 1.5](#).

SUTENT[®] (sunitinib malate) was approved by the Food and Drug Administration (FDA) and the European Medicines Agency in 2006 in oral capsule form for the treatment of gastrointestinal stromal tumor and renal cell carcinoma, and in 2011 for the treatment of pancreatic neuroendocrine tumor and represents a class of small molecules referred to as receptor tyrosine kinase inhibitors (TKIs).

Sunitinib malate is a small molecule (532.6 g/mol) and is a multiple receptor TKI that prevents receptor phosphorylation and “turns off” the downstream effects of selected receptors, particularly all the vascular endothelial growth factor receptors (VEGFR-1, -2, and -3) ([Figure 1-1](#)) which are known to influence macular edema. GB-102 offers the potential for more complete blockade of VEGF-mediated angiogenesis compared to blockade of VEGF-A ligand alone (eg, aflibercept, bevacizumab, or ranibizumab). A full description of sunitinib is provided in the Investigator’s Brochure.

Figure 1-1. Sunitinib Mechanism of Action

1.5 General Information

1.5.1 Nonclinical Studies

Sunitinib malate has been evaluated in nonclinical safety studies in compliance with International Council for Harmonisation (ICH) guidelines to support its approval for cancer indications (**SUTENT[®]**). Nonclinical IND-enabling studies describing SUTENT's primary and secondary pharmacodynamics, safety pharmacology, pharmacokinetics (PK), toxicology/toxicokinetics (single and repeat dose), genotoxicity, reproductive toxicity, phototoxicity, and local tolerance (dermal and ocular) have been published in the literature and can be referenced in the Investigator's Brochure for GB-102 (IB).

A summary of the ocular pharmacology, tissue PK, and toxicology for GB-102 and sunitinib follows.

1.5.1.1 Primary Pharmacology - Ocular

Sunitinib has demonstrated evidence of inhibiting angiogenesis, vascular permeability, proliferation, and fibrosis – key findings associated with DME, RVO, and choroidal neovascular lesions in neovascular age-related macular degeneration (nAMD).

Sunitinib has also demonstrated evidence in neuroprotection.

[figure not shown]
Single Intravitreal Administration of GB-102 Reduces VEGF-induced Leukostasis and Retinal Nonperfusion

VEGF plays a critical role in the pathogenesis of diabetic retinopathy as well as nAMD. Increased levels of VEGF in the retina cause leukocytic plugging and closure of retinal vessel exacerbating retinal hypoxia, the main driver of progression of DR. Adult rho/VEGF mice were given an intravitreal injection of 10 µg sunitinib (GB-102) or 40 µg of aflibercept in one eye and an equivalent mass of empty microparticles (MPs) or phosphate buffered saline (PBS) in the

fellow eye. After one week, mice were perfused with PBS through the left ventricle to remove all non-adherent erythrocytes and leukocytes, and then perfused with FITC-concanavalin A to stain remaining adherent leukocytes. Compared with eyes injected with empty MPs, those injected with sunitinib MPs had a significant reduction in the mean number of adherent intravascular leukocytes (Figure 1-2A). Similarly, aflibercept-injected eyes had a significant reduction in the mean number of adherent intravascular leukocytes compared with PBS-injected eyes.

Rho/VEGF mice also had fluorescein angiography at baseline and then were given an intravitreal injection of 10 µg of sunitinib (GB-102) in one eye and 10 µg of empty MP in the other eye. Some areas of retinal nonperfusion at baseline showed improved perfusion 1 week after injection of GB-102, but this was not seen in empty MP-injected eyes (Figure 1-2B) (Data on file, 2019)

Figure 1-2. Intravitreal Injection of GB-102 in rho/VEGF Mice Reduces Leukocytes and Improves Retinal Perfusion

[figure not shown]

*p < 0.001 by Mann Whitney for difference from corresponding fellow eye control.

Oral Sunitinib Malate Inhibits Choroidal Neovascularization (CNV) in a Murine Laser Injury Model

The initial evidence to demonstrate the ability of sunitinib malate to inhibit choroidal neovascular permeability was in a laser-induced CNV mouse model (Takahashi 2006). Three groups of mice (N = 5 per group) were orally administered 40, 80, 150 mg/kg sunitinib malate or vehicle for 5 days following laser endophotocoagulation of the retina and Bruch's membrane. Permeability leakage of the CNV lesions was assessed by fluorescein angiography (FA) *in vivo*. Volume of the CNV lesions was quantified histologically in ocular cross-sections. The authors reported a dose-response in both the FA scores and histologic CNV lesion volume compared with vehicle control (Figure 1-3).

Figure 1-3. Oral Dosing of Sunitinib Reduces Laser-Induced Choroidal Neovascularization in a Murine Model

CNV = choroidal neovascularization; FA = fluorescein angiogram

(A) FA

(B) FA scores

[figure not shown]
(C) CNV histology scores

Source: Takahashi, 2006

Single Intravitreal Administration of GB-102 Demonstrates Sustained Inhibition of CNV in a Murine Laser Injury Model for Up to 6 Months

The murine model of laser-induced rupture of Bruch's membrane results in CNV that is similar to type 2 CNV in patients with nAMD, because the new vessels originate from the choroid and penetrate through Bruch's membrane and the retinal pigmented epithelium (RPE) into the subretinal space (**Data on file, 2019**). Studies in this model helped to implicate VEGF as a critical stimulus for nAMD and predicted the clinical benefits seen with aflibercept, a recombinant VEGF-neutralizing protein commonly used to treat patients subjects with nAMD. In order to assess the efficacy of GB-102 microparticles (MPs) over time, C57BL/6 mice were given an IVT injection of microparticles (MPs) containing 10 μ g sunitinib in one eye and empty MPs in the fellow eye and then had laser-induced rupture of Bruch's membrane at 3 locations in each eye at time points ranging from 1 to 24 weeks after injection. Compared with empty MP fellow eye controls, the mean area of CNV at Bruch's membrane rupture sites was significantly less in eyes injected with MPs containing 10 μ g sunitinib at each time point through week 24 (**Figure 1-4**). There was significant suppression of CNV 0.5 months after injection of 40 μ g of aflibercept, but not 2 months or 3.5 months after injection.

Figure 1-4. Sustained Reduction in Laser-Induced CNV Following Single Injection of IVT GB-102 Compared to IVT Aflibercept

[figure not shown]
Sunitinib Exhibits In Vitro and In Vivo Neuroprotective Effects in Photoreceptors and Retinal Ganglion Cells

Sunitinib malate was identified as one of the most potent small molecules in promoting retinal ganglion cell (RGC) survival and neurite outgrowth following high through-put screening of various small molecule libraries (Zack 2011). The neuroprotective effects of sunitinib appear to reduce stress-induced apoptosis of RGCs in models of ischemia and optic nerve crush injury (Sharma 2011). Sunitinib also promotes photoreceptor survival and function as demonstrated in a murine light damage model of retinal degeneration (Kim 2015).

Intravitreal GB-102 has been shown to reduce photoreceptor death in preclinical murine models of Type 3 CNV (Figure 1-5) (Data on file, 2019). Rho/VEGF mice were given an intravitreal injection of 10 µg of sunitinib microparticles (GB-102) in one eye and 10 µg of empty MP in the other eye or 40 µg of aflibercept in one eye and PBS in the fellow eye. At P42, mice (n=7 for each group) were euthanized and serial frozen ocular sections were cut from the superior pole of the eye (S0) to the inferior pole (I0) and sections 25% (S1 and I1), 50% (S2 and I2), and 75% (S3 and I3) of the distance between each pole and the optic nerve (ON) were stained with hematoxylin and outer nuclear layer (ONL) thickness was measured by image analysis by a masked investigator. The ONL of sections from the S2 location of GB-102-injected eyes appeared thicker than those from empty MP-injected eyes, but those from aflibercept-injected eyes appeared similar to those from PBS-injected eyes (Figure 1-5A). The mean (±SEM) ONL thickness was significantly greater at 3 of 6 locations in GB-102-injected eyes compared with

empty MP-injected eyes, but there was no difference between aflibercept- and PBS-injected eyes (Figure 1-5B). At P49, mice (n=5 for each group) were euthanized and immunoblots of retinal homogenates from GB-102-injected eyes showed prominent bands for rhodopsin kinase (GRK-1) (Figure 1-5C). Densitometry showed that the mean (\pm SEM) GRK-1/Actin ratio was significantly greater in retinas from GB-102-injected eyes compared with empty MP-injected fellow eyes, but not aflibercept-injected eyes versus PBS-injected fellow eyes (Figure 1-5D).

Figure 1-5. Single Injection of Intravitreal GB-102 Reduces Photoreceptor Death in Rho/VEGF Mice with Type 3 CNV

**p<0.01 by Mann Whitney for difference from fellow eye empty MP control.

1.5.1.2 Pharmacokinetics of Intravitreal Administration of GB-102 – Preclinical Studies

[figure not shown]
Single Intravitreal Injection of GB-102 Sustains Inhibitory Levels of Drug in the Retinal Pigment Epithelium-Choroid up to 6 Months in Pigmented Rabbits up to 6 Months

Ocular tissue PK was conducted in male pigmented New Zealand rabbits receiving a single IVT administration of sunitinib malate GB-102 (1.0 mg/eye). Tissue levels of drug were determined in the posterior segment (retina, RPE-choroid, vitreous humor) and anterior segment (cornea, iris-ciliary body, and lens) as determined by liquid chromatography/tandem mass spectrometry at various time points (Peterson 2016).

Following injection, sunitinib drug levels are highest in tissues containing melanin pigment (Figure 1-6). Tissue drug levels, in descending order, are as follows: RPE-choroid > iris-ciliary body > retina/lens > cornea > vitreous. There were no toxicological concerns related to pigment-binding discovered during preclinical testing. Drug concentrations of sunitinib are present in RPE-choroid and retina at 2- to 3-log orders higher than the kinetic inhibition constant to suppress VEGFR through 6 months. The depot is fully resorbed by 12- to 14-weeks on ophthalmic examination. The sustained drug levels in the posterior segment tissue following resorption of the depot is attributed to the secondary reservoir effect of the RPE-choroid (melanin binding).

Sunitinib was cleared from posterior segment ocular tissues with an average half-life of approximately 19 days with a range of 2-3.5 weeks. Peak exposure (T_{max}) was typically within 3 to 4 months for retina and RPE-choroid, whereas vitreous T_{max} occurred at 1 month. Given a T_{max} at 3 to 4 months and a half-life of 0.64 months, sunitinib would be cleared from the posterior segment ocular tissues within 6 to 8 months.

Figure 1-6. Ocular Tissue Drug Levels of Sunitinib Following a Single Intravitreal Injection of 1.0 mg GB-102 in Pigmented New Zealand Rabbits

No Systemic Levels of Sunitinib Are Detected Following a Single Intravitreal Injection of 2 mg Dose/Eye of GB-102 in Pigmented Rabbits

A Good Laboratory Practice (GLP) plasma toxicokinetics study was conducted in Dutch belted rabbits receiving a single IVT administration of a 2.0 mg/eye dose of GB-102 (50 μ L) (CRL Report 5700643). Plasma samples were assayed for sunitinib (lower limit of quantitation [LLQ] > 0.3 ng/mL) predose and on Days 1, 2, 7, 16, 37, and 99 postdose. No measurable levels of sunitinib were detected systemically at any time point.

1.5.1.3 Toxicology

Sunitinib malate was originally developed as an orally administered agent for the treatment of advanced malignancies at a daily dose of 37 to 50 mg (SUTENT® capsules). The steady state plasma levels of sunitinib at the oral recommended daily dose is approximately 60 to 100 ng/mL. Based on allometric scaling from nonclinical ocular PK studies (rabbits, rats) to humans, it is estimated that a single orally administered approved dose of 50 mg sunitinib in man results in uveal tissue concentration of drug that are 1-log to 2-log orders higher than a single IVT injection of GB-102 containing 1 mg sunitinib (Peterson 2016, Speed 2012).

Three GLP ocular toxicology studies were conducted with GB-102: a single dose study in rabbits, a repeat dose study in rabbits, and a repeat dose study in minipigs.

The ocular toxicity following a single IVT injection (50 µL) of GB-102 at doses of 0, 0.25, 0.5, 1.0, and 2.0 mg/eye in pigmented rabbits was evaluated in a GLP study with up to 19 weeks observation. Assessments were conducted with *in vivo* ophthalmic examination, including ERGs, and postmortem histopathology of the enucleated eyes. The main findings included 1) time- and dose-dependent lens opacities, which were due to the high injection volume (50 µL), and 2) mild anterior and vitreous inflammation, which was due to endotoxin contamination of the test materials.

In the repeat-dose rabbit study, animals received IVT injections of 0.125, 0.25 and 0.5 mg/eye GB-102 (in volumes up to 12 µL). Animals were injected on Day 1 and Day 141 over the course of 40 weeks. GB-102 was well tolerated compared to the GLP single dose ocular toxicology study in rabbits. The main findings in the repeat dose rabbit study included transient ocular inflammation at all dose levels regardless of dose volume, which was not test article related. Focal, peripheral and inferior lens opacities occurred in 3 out of 4 groups, which were test article related.

In the repeat dose minipig study, animals received IVT injections of 0.25, 0.5, and 1 mg/eye GB-102 (in volumes up to 24 µL). Animals were injected on Day 1 and Day 141 over the course of 40 weeks. GB-102 was well tolerated based on all endpoint assessments including no findings on histology. There were no clinical observations of adverse events and no test article-related effects on hematology, coagulation or clinical chemistry parameters, which is consistent with a lack of detectable systemic exposure. The clinical ocular examination observations were limited to a transient, yellow discoloration of the vitreous humor and lens in some animals and there were no test article-related microscopic findings. Therefore, the no-observed-adverse-effect-level (NOAEL) is above the highest dose (1 mg/eye) tested in this study.

Overall, toxicology results indicate that IVT injections of GB-102 twice with a 5-month interval and up to a 10-month observation period in rabbits or minipigs at a corresponding injection volume in the clinic, was well tolerated in the eyes and supports IVT administration of up to 2 mg GB-102 every 6 months in the clinic.

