4.4 Exclusion Criteria

1. History, within 6 months prior to screening, of any of the following: myocardial infarction, any cardiac event requiring hospitalization, treatment for acute congestive heart failure, transient ischemic attack, or stroke
2. Uncontrolled hypertension with systolic blood pressure ≥ 160 mmHg and/or diastolic blood pressure ≥ 95 mmHg at the Screening Visit
3. Uncontrolled diabetes mellitus, defined as hemoglobin A1c $>12.0\%$ at the Screening Visit
4. Chronic renal disease requiring chronic hemodialysis or renal transplantation
5. Participation in any investigational study within 30 days prior to screening, or planned use of an investigational product or device during the study; any exposure to a prior investigational drug product must be fully washed out (at least 5 half-lives)
6. Previous participation in an investigational study of GB-102
7. Spherical equivalent of the refractive error in the **study eye** demonstrating more than -6 diopters of myopia (prior to cataract or refractive surgery) at the Screening Visit
8. Uncontrolled IOP, defined as an IOP > 25 mmHg, despite antiglaucoma medications in the **study eye** at the time of screening or controlled glaucoma that requires management with > 2 topical hypotensive medications

9. Presence of any clinically significant epiretinal membrane or vitreomacular traction in the **study eye**
10. History or evidence of any of the following in the **study eye**:
 - a. Macular surgery or other surgical intervention for AMD
 - b. Prior retinal detachment
 - c. Vitrectomy
 - d. Retinal laser treatment with the exception of prior laser photocoagulation for treatment of diabetic retinopathy
 - e. Glaucoma filtering surgery (eg, trabeculectomy) or glaucoma drainage device (eg, Ahmed valve or Baerveldt valve) including minimally invasive glaucoma shunts (eg, minimally invasive glaucoma surgery) prior to the Screening Visit. Selective laser trabeculoplasty (SLT) ≥ 3 months prior to Screening Visit is allowed.
 - f. Cataract surgery within the 3 months prior to the Screening Visit
 - g. Neodymium:yttrium-aluminum-garnet (Nd:YAG) laser capsulotomy within the 30 days prior to the Screening Visit. Note: prior Nd:YAG laser posterior capsulotomy in association with a posterior intraocular lens implantation is allowed.

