- An important medical event or serious medical condition that does not meet any of the above criteria may be considered an SAE if, based upon appropriate medical judgment, it jeopardizes the subject or requires medical or surgical intervention to prevent one of the outcomes listed above. Examples of such medical events include allergic bronchospasm requiring intensive treatment in an emergency room or at home, blood dyscrasias, or convulsions that do not result in in-patient hospitalization, or the development of drug dependency or drug abuse.

An overall summary will be presented that includes the number of TEAEs and the number and percentage of subjects who experienced at least one TEAE, total and by cohort. This summary will also include breakdowns of TEAEs further categorized as ocular (study eye and non-study eye, separately), non-ocular, serious TEAEs, TEAEs by maximum severity, treatment-related TEAEs, and TEAEs leading to subject withdrawal.

Additional summaries of TEAEs will be provided showing the number and percentage of subjects who experienced at least one TEAE and total number of events. These summaries will be presented by SOC and PT. Non-ocular TEAEs will be summarized using discrete summary statistics and presented by cohort and total subjects at the subject and event level by SOC and PT. Ocular TEAEs will be similarly summarized at the subject level for study and non-study eyes separately. If a subject has multiple TEAEs coded to the same PT within same SOC, that PT will only be reported once. As with the PT, if a subject reports multiple conditions within the same SOC, that SOC will only be reported once at the subject level. In the summary, SOCs are listed in order of decreasing frequency for total subjects. PTs are listed in order of decreasing frequency within each SOC for total subjects. The occurrence of non-ocular and ocular TEAEs will also be tabulated by SOC and PT for the following: maximal severity and suspected relationship to study drug.

Separate summaries will be provided for the following categories of AEs:

- Ocular TEAEs in the study eye
- Ocular TEAEs in the non-study eye
- Non-ocular TEAEs
- Treatment-related ocular TEAEs in the study eye
- Treatment-related ocular TEAEs in the non-study eye
- Treatment-related non-ocular TEAEs
- Ocular serious TEAEs in the study eye
- Ocular Serious TEAEs in the non-study eye
- Non-ocular serious TEAEs
- Treatment-related ocular serious TEAEs in the study eye

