### 13.3 Slit-Lamp Biomicroscopy Examination

A slit-lamp biomicroscopy examination of the eyelid, cornea, conjunctiva, anterior chamber, iris, pupil, lens, lens status, and Age-Related Eye Disease Study (AREDS) scores for Nuclear, Cortical, and PCS opacity will be performed at each visit. The results will be graded as normal, abnormal not clinically significant (NCS), or abnormal clinically significant (CS) for all but the lens status and AREDS scores. Lens status will be denoted phakic, pseudophakic, or aphakic. AREDS opacity scores are <1, 1, 1.5, 2, 2.5, 3, or >3. Anterior chamber cells and flare will also be assessed using categorical responses that range from 0 to 4+, as described below.

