#### Anterior Chamber Flare:

| Grade | Description                           |
|-------|---------------------------------------|
| 0     | None                                  |
| +1    | Trace                                 |
| +2    | Moderate (iris and lens detail clear) |

- +3 Marked (iris and lens detail hazy)
- +4 Intense (fibrin or plastic aqueous)

The results will be summarized using counts and percentages for each cohort and for all GB-102 treated subjects combined at each visit for each eye (study eye and non-study eye). Percentages will be based on the number of subjects in each cohort with responses. Shift tables for each biomicroscopy parameter will also be provided comparing each follow-up visit to baseline. A subject listing of the slit-lamp biomicroscopy parameters will also be produced.

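### The protocol blames a fixed 50 µL volume for lens opacities that rose with dose, and no planned safety table shows lens events among eyes that still have a natural lens

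*Protocol*

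**What the plan says.** **Toxicology background (Protocol 1.5.1.3).** The first rabbit study is described as a "single IVT injection (50 µL) of GB-102 at doses of 0, 0.25, 0.5, 1.0, and 2.0 mg/eye". Its main lens finding is "time- and dose-dependent lens opacities, which were due to the high injection volume". The second rabbit study used two injections of lower doses, "in volumes up to 12 µL", and reports: "Focal, peripheral and inferior lens opacities occurred in 3 out of 4 groups, which were test article related". Both arms of this trial receive 50 µL and differ only in dose, 1 mg or 2 mg (Protocol 3.1).

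**Eligibility and assignment.** Protocol 4.4 (criterion 11) excludes anterior chamber lenses, aphakia and a breached posterior capsule, but not an ordinary posterior chamber implant. Criterion 10g states that "prior Nd:YAG laser posterior capsulotomy in association with a posterior intraocular lens implantation is allowed". Protocol 5.2.2 fills the two arms by consecutive enrolment and does not balance them on lens status.

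**Analysis.** SAP 13 puts all safety analyses on the safety set. SAP 13.1 gives the "number and percentage of subjects who experienced at least one TEAE, total and by cohort". In SAP 13.3, "Lens status will be denoted phakic, pseudophakic, or aphakic", and AREDS opacity scores are recorded at each visit. Percentages there use subjects with a response, and "Shift tables for each biomicroscopy parameter will also be provided comparing each follow-up visit to baseline". No listed table is limited to eyes phakic at baseline, and no rule covers an eye without a natural lens.

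**The concern.** Of the findings reported in Protocol 1.5.1.3, lens opacity is the one described as increasing with dose, and dose is the only planned difference between the arms. Two things follow.

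First, the text assigns the finding to volume, which does not vary between the arms, and so leads the reader away from the factor that does. Investigators classify each event as related or not, and weigh alternative causes when they do so (Protocol 8.3).

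Second, the lens data are collected, but no planned table shows lens events by dose among the eyes that can have them. With about 10 subjects per arm and no balancing, the number of phakic eyes could differ between arms. Readers of a descriptive safety report will compare the raw percentages.

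**Working it through.** **1. Does volume explain the gradient?** In the single-dose study, dose runs from 0.25 to 2.0 mg/eye, an 8-fold range (2.0 / 0.25), plus a 0 mg group. Volume is listed once, at 50 µL. A factor with a single value cannot by itself produce a response that rises with dose; if volume were the only cause, the 0 mg group should look like the 2.0 mg group. Incidence by group is not given, so this cannot be checked. In the repeat-dose study, opacities attributed to the test article occurred at no more than 12/50 = 24% of that volume. That study had two injections over 40 weeks, its volumes were not all equal, and no gradient is reported. It is therefore evidence against a volume-only cause, not a direct test of it.

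**2. The plan's own safety figure.** Protocol 9.4 says that adverse event rates above 15% overall and 30% per dose are detectable with about 95% confidence.
- Rule of three: 3/20 = 15% and 3/10 = 30%. Both are reproduced.
- Exact probability of at least one event: 1 − 0.85^20 = 96.1% and 1 − 0.70^10 = 97.2%.

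For a lens event only phakic eyes count. The phakic share is not in the documents; I assume 4 to 10 phakic eyes per arm.

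| Phakic eyes in an arm | P(at least 1 event) at a true 30%: 1 − 0.7^n | Rate detectable with 95% probability: 1 − 0.05^(1/n) |
|---|---|---|
| 10 | 97.2% | 25.9% |
| 8 | 94.2% | 31.2% |
| 6 | 88.2% | 39.3% |
| 4 | 76.0% | 52.7% |

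**3. Dilution in the adverse event tables.** Rate shown = rate among phakic eyes × phakic share.
- Two events in each arm of 10: 2/10 = 20% against 2/10 = 20%. With an assumed 8 and 4 phakic eyes: 2/8 = 25% against 2/4 = 50%.
- An assumed true contrast of 20% against 60% (40 points), with phakic shares of 80% and 40%: 0.20 × 0.80 = 16% against 0.60 × 0.40 = 24%, so 8 points are shown.
- With equal shares of 70%: 14% against 42%, so 28 points are shown.

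**4. AREDS summaries by visit.** The SAP leaves two readings open.
- Eyes without a natural lens receive a score. They then dilute the summary, but an operated eye stays in.
- They receive no score. Pseudophakic eyes then do not dilute, but an operated eye leaves later visits. With an assumed 3 progressing eyes among 6 phakic eyes (3/6 = 50%), 1, 2 or 3 operations among those three give 2/5 = 40%, 1/4 = 25% or 0/3 = 0% at Month 6.

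**5. The lens scale.** Protocol 18.5.1 to 18.5.3 grade each opacity +1, +2 or +3, where +1 means no opacity. SAP 13.3 uses <1, 1, 1.5, 2, 2.5, 3 and >3. Four of these seven values (<1, 1.5, 2.5, >3) have no definition in the protocol.

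**The case against.** The strongest reply is that the planned tables contain no error. The percentage of all treated subjects is a correct incidence for the safety set, the trial tests no hypothesis, and the arms are open-label and not described as randomized. Slit-lamp grades are listed in SAP 3 under other variables; the primary endpoint is the occurrence of adverse events. With about 20 subjects, a reader can work out the phakic denominators from the listings. Inclusion criterion 9 and exclusion criterion 12g remove eyes with vision-affecting opacity at entry, and follow-up is only 180 days. The minipig study had no microscopic findings related to the test article. All of this stands, and it is why the new table should supplement the planned ones.

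The illustration is also thin: 2/8 against 2/4 gives a two-sided Fisher p of about 0.55. It shows what a mixed denominator can hide, not that a dose effect would be established.

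A reader might infer more than the documents support:
- *That the SAP drops operated eyes from the shift tables.* No text says so. The rule about subjects with responses is attached to the counts and percentages, and the denominator of the shift tables is not given.
- *That dilution and drop-out both affect the AREDS tables.* They depend on opposite coding choices, so they cannot both affect the same table.
- *That the signal is lost.* A reported cataract event stays in the cohort's adverse event tables after surgery, and the slit-lamp and procedure listings (16.2.8.2, 16.2.4.10) show the eye. Lens status also falls under the shift-table rule for each parameter, although the titles of Tables 14.3.9.2 and 14.3.9.3 do not name it.
- *That investigators are told to rule out the drug.* The next paragraph of Protocol 1.5.1.3 openly names the test article, and Protocol 8.3 asks about the study procedure as well as the drug.

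**Conclusion.** The point holds in two parts of different weight.

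The toxicology text does not fit its own design. A volume common to all doses is given as the cause of a finding that rose with dose, and the next study weakens that explanation. Calling the two studies a formal contradiction would go too far, because they are different experiments. Nor does the text prove a drug effect on the lens; it means only that such an effect is not excluded. The passages must be reconciled.

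The SAP part is an omission that is cheap to repair. Cataract percentages by dose will include eyes not at risk, and the treatment of AREDS grades in eyes without a natural lens is unspecified. The possible effect is masking, such as 20% against 20% standing for 25% against 50%. Reversal should not be claimed: none of the worked cases shows it, and with true rates of 20% and 60% it would need a phakic share in the 1 mg arm more than three times that in the 2 mg arm. All sizes rest on assumed phakic shares, event counts and numbers of operations.

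**What to change.** 1. In Protocol 1.5.1.3, reconcile the two attributions. State that volume was the same at all doses in the single-dose study, and that a test-article effect on the lens is not excluded. Incidence by group, including the 0 mg group, would settle most of the question if it is available.
2. Keep the planned safety-set tables. Add to SAP 13.1 and 13.3 one supplementary table by dose, limited to study eyes phakic at baseline, with: (a) lens and cataract TEAEs; (b) any worsening, yes or no, of the worst post-baseline lens grade against baseline. Count removal of the lens for new or progressed cataract after dosing as worsening. Show the phakic fellow eye alongside as context.
3. State in SAP 13.3 how an eye without a natural lens is coded for AREDS, and how an eye is handled after cataract surgery during the study.
4. Bring the lens scale in Protocol 18.5 and SAP 13.3 into agreement before the grades are tabulated.

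The cost is background wording, a few SAP sentences and one small table from data already collected in both eyes at every visit. The downside is a smaller denominator and a less precise rate in each arm, so counts should stand beside percentages. The comparison of doses remains descriptive.
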